### 6.5 Pre-Discharge Visit (In-hospital)

Same day discharge after the ablation procedure is not recommended for the study, even if it is considered standard of care at some institutions. Active surveillance of the subject's postoperative care and condition is recommended for at least 72-hours or prior to discharge, whichever occurs first.

The following are required testing for the Pre-Discharge Visit:

- Complete physical exam and 12-lead ECG
- Neurological assessment as recommended in the 2017 Consensus Statement
- Document AAD and anticoagulant drug usage
- Document adverse events and protocol deviations

If the subject requires an extended hospitalization due to a complication or other reason, all pre-discharge testing should be performed prior to discharge, but no later than 72 hours post-procedure.

### 6.6 Blanking and Therapy Consolidation Periods

A blanking period of 90-days will be employed after the initial ablation procedure, followed by a 90-day therapy consolidation period and then a 9-month evaluation period for a total of 15-months of follow-up.

## Clinical Investigation Plan

Early recurrence of AF, AFL, or AT within the blanking period or therapy consolidation period will not be considered treatment failures. During the blanking and therapy consolidation periods, adjustment of antiarrhythmic medications, cardioversions, and one repeat ablation procedure may be performed.

### 6.7 Follow-up Assessments

Subjects will undergo the following assessments described below at 7-14 days and at 3, 6, 12 and 15-months post-ablation.

#### 7-14 Day Follow-up Visit

This visit constitutes a phone call to the subject after each ablation procedure (initial and if applicable, a repeat procedure). This visit may also be conducted in-person at the site. Documentation for the trial consists of the following:

- Document AAD and anticoagulant drug usage
- Document adverse events and protocol deviations

#### 3-Month (91 + 21 days) Follow-Up Visit

The 3-month follow-up visit is a scheduled in-person site visit. When subjects are seen at the 3-month visit, it is recommended that they are weaned off AADs during the therapy consolidation period if they are doing well and have not discontinued these medications prior to this visit.

- Perform 12-lead ECG
- Document AAD and anticoagulant usage
- Administer the EQ-5D-5L questionnaire as defined in **Section 6.7.2**
- Document adverse events and protocol deviations
- It is recommended to provide the subject with an event monitor for recording at regular intervals (e.g. monthly) and/or for symptomatic events through the 15-month visit.
- It is recommended that a 24-hour Holter be performed
- After the 3-month visit through the end of the study, any signs or symptoms of AF/AFL/AT recurrence should be recorded, and the subject should have either a 12-lead ECG or other form of ECG monitoring per the site's standard practice to determine if recurrence has occurred.

#### 6-Month (181 + 30 days) Follow-Up Visit

The 6-month follow-up visit is an in-person site visit.

- Perform 12-lead ECG
- Document AAD and anticoagulant usage
- Administer the EQ-5D-5L questionnaire as defined in **Section 6.7.2**
- Document adverse events and protocol deviations
- If there are symptoms of AF/AFL/AT present, the subject should have either a 12-lead ECG or other form of ECG monitoring to document the AF/AFL/AT recurrence

## Clinical Investigation Plan

- Administer a 24-hour Holter monitor provided by the core laboratory (required) Document any recurrences including details of any repeat electrophysiology studies

### **12-Month (365 ± 30 days) Follow-Up Visit**

The 12-month follow-up visit is an in-person site visit.

- Perform 12-lead ECG
- Document AAD and anticoagulant usage
- Administer the EQ-5D-5L questionnaire as defined in **Section 6.7.2**
- Document adverse events and protocol deviations
- If there are symptoms of AF/AFL/AT present, the subject should have either a 12-lead ECG or other form of ECG monitoring to document the AF/AFL/AT recurrence
- It is recommended that a 24-hour Holter be performed
- Document any recurrences including details of any repeat electrophysiology studies

### **15-Month (450 ± 30 days) Follow-Up Visit**

The 15-month follow-up visit is a scheduled in-person site visit.

- Perform 12-lead ECG
- Document AAD and anticoagulant usage
- Administer the EQ-5D-5L questionnaire as defined in **Section 6.7.2**
- Document adverse events and protocol deviations
- If there are symptoms of AF/AFL/AT present, the subject should have either a 12-lead ECG or other form of ECG monitoring to document the AF/AFL/AT recurrence
- Document any recurrences including details of any repeat electrophysiology studies
- Administer a 24-hour Holter monitor provided by the core laboratory (required)

#### **6.7.1 Unscheduled Visits**

If a subject is seen by any physician for possible AF recurrence and/or arrhythmia associated symptoms outside of a regularly scheduled study visit and/or had an urgent care or emergency room visit regarding possible arrhythmia recurrence, these visits need to be documented as “Unscheduled Visits”, unless the visit is already documented on an Adverse Event CRF. If there is an Adverse Event associated with this visit, then an Unscheduled Visit CRF does not need to be completed.

Minimally, the following information should be documented for an unscheduled visit.

- 12-lead ECG, if performed during the visit
- Document AAD and anticoagulant usage
- Document adverse events and protocol deviations

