## Clinical Investigation Plan

### 5.5 Subject Withdrawal

Each enrolled subject shall remain in the clinical investigation until completion of the required follow-up period. However, a subject's participation in any clinical investigation is voluntary and the subject has the right to withdraw at any time without penalty or loss of benefit. Conceivable reasons for discontinuation may include, but not be limited to, the following:

- Death
- Voluntary withdrawal
- Lost to follow-up (described below)
- Subject's following is terminated according to **Section 3.3**

The Sponsor must be notified of the reason(s) for subject discontinuation. The site will provide this information to the Sponsor as documented on the appropriate CRF. Investigators must also report this to their respective IRB/EC as defined by their institution's procedure(s).

No additional follow-up will be required or data recorded from subjects once they are withdrawn from the clinical investigation, except for the status (deceased/alive). If a subject withdraws from the investigation due to problems related to the safety or performance of the device under investigation, they will be followed by their regular physician per their standard of care.

If for any reason, the subject has the TactiCath SE inserted into their vasculature, but no ablation was performed, and the subject will not be rescheduled to receive another ablation procedure, the subject will be followed for 30-days to assess safety and then exited from the trial.

In the event that a subject does elect to withdraw from the trial, the site should make attempts to schedule the subject for a final visit. At this final follow-up visit, the subject will undergo assessments as outlined for an unscheduled visit (**Section 6.7.1**) if the visit does not coincide with a scheduled follow-up visit.

Withdrawn subjects count towards the total enrollment at the site and will not be replaced by enrolling additional subjects.

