#### 8.2.2 Additional Data Analyses

Additional data to be collected in this clinical investigation are described and will be reported using summary statistics. No hypothesis tests will be performed.

In general, continuous (CONT) variables will be summarized with the numbers of observations, means with standard deviations, quartiles, minimums, maximums as per the table mockups.

Categorical (CAT) variables will be summarized with subject counts and percentages/rates, and where specified in the table mockups.

Survival (SURV) analysis will be conducted to analyze time-to-event variables. Subjects without events will be censored at their last known event-free time point. Subjects withdrawn or otherwise lost to follow-up during the follow-up period will be censored at their last known visit. Survival data will be presented using the Kaplan-Meier product limit method.

The following list of analyses describes how the additional evaluations will be analyzed:

- Acute procedural success, defined as confirmation of entrance block in all pulmonary veins (CAT)
- Proportion of subjects off all Class I or III AADs taken to treat AF/AFL/AT at 15-months (SURV)
- Proportion of subjects who achieve 15-month single procedure success, defined as freedom from documented AF/AFL/AT recurrence (episodes >30 seconds) during the 9-month period following the blanking and therapy consolidation periods after a single ablation procedure (SURV)
- 
- Changes in EQ-5D-5L scores from baseline to follow-up at 3, 6, 12, and 15-months after the initial procedure (CONT)

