### 8.7 Procedures for Accounting for Missing Data

Every effort will be made to collect all required data. All data available for the endpoints specified among the analysis population will be used. Missing data will not be imputed. Kaplan-Meier analysis will censor subjects withdrawn or otherwise lost-to-follow-up at last known visit.

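### A subject who withdraws between scheduled visits needs no rhythm recording unless symptomatic, yet is censored as recurrence-free at that exit visit

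*Combined protocol and SAP*

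**What the plan says.** **Exit visit.** Section 5.5 says of a subject who elects to withdraw that "the site should make attempts to schedule the subject for a final visit". It continues: "At this final follow-up visit, the subject will undergo assessments as outlined for an unscheduled visit", but only "if the visit does not coincide with a scheduled follow-up visit". After withdrawal, section 5.5 allows nothing further to be recorded except whether the subject is alive.

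**Content of an unscheduled visit.** The minimum list in section 6.7.1 has three items: drug use, adverse events and deviations, and "12-lead ECG, if performed during the visit". It contains no Holter.

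**Symptomatic subjects.** The 3-month visit section covers signs or symptoms of recurrence from that visit to study end, and says that "the subject should have either a 12-lead ECG or other form of ECG monitoring".

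**Censoring.** Section 8.2.2 states: "Subjects withdrawn or otherwise lost to follow-up during the follow-up period will be censored at their last known visit". Section 8.7 repeats it: "Kaplan-Meier analysis will censor subjects withdrawn or otherwise lost-to-follow-up at last known visit", and rules out imputation. The sentence just before the rule in 8.2.2 uses a different cut-off for subjects without events, namely the latest time at which they are known to be event-free. It does not say what evidence makes a time event-free, or which rule governs a withdrawn subject.

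**Endpoint.** Single-procedure success at 15 months (8.2.2, time-to-event) requires a recurrence to be documented, with an episode longer than 30 seconds, during the nine months after the blanking and therapy consolidation periods.

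**The concern.** Read together, these rules let a visit without any rhythm information set the date to which a subject is treated as recurrence-free. The gap cannot be closed later. A recurrence counts only if documented, and no rhythm data are collected after withdrawal, so the exit visit is the last opportunity.

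The other safeguards are thin between visits. Holters are required only at 6 and 15 months, and event monitors are recommended rather than required.

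The direction of error is a worry because return of AF is a plausible reason to leave the study. Section 1.1.1 describes effectiveness as the main purpose, and section 1.1.2 says the data will support a persistent AF indication in China and other countries. With about 100 subjects, a few unobserved failures can move the curve visibly.

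**Working it through.** The plan gives no figure for this point, so there is none to reproduce. Section 4.0 makes all endpoints non-powered.

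**1. Length of the untested interval.** Inputs are the visit days in section 6.7 and Table 2: 6 months = day 181, 12 months = day 365 ± 30, 15 months = day 450 ± 30. Each of these visits includes a 12-lead ECG.
- After the 6-month ECG, up to the day before the 12-month window opens: 365 − 30 − 1 = 334, and 334 − 181 = 153 days. Against the 270 evaluation days (181 to 450), 153/270 = 57%.
- After a nominal 12-month ECG, up to the day before the 15-month window opens: 450 − 30 − 1 = 419, and 419 − 365 = 54 days (84 if the 12-month visit was on day 335).
- If the 6-month visit was on day 151, which Table 2's ± 30 permits, the gap is 334 − 151 = 183 days. The first 30 of those precede the evaluation period.

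**2. Days on which the gap can arise.** If an exit visit inside a scheduled window counts as coinciding with that visit, the windows cover days 181–211, 335–395 and 420–450: 31 + 61 + 31 = 123 days, or 123/270 = 46% of the evaluation period. The gap concerns the remaining days.

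**3. Count of missed recurrences.** Assume *w* withdrawals at mid-period, unrelated to recurrence; 15-month recurrence *p* of 30% or 50% at a constant hazard; and a silent share *s* of 30% or 60%. Expected missed = *w* × (1 − (1 − *p*)^0.5) × *s*. For *w* = 10:
- low: 10 × (1 − 0.7^0.5) × 0.3 = 0.5
- high: 10 × (1 − 0.5^0.5) × 0.6 = 1.8

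**4. Effect on the Kaplan-Meier estimate.** This is an illustrative simulation with 100 subjects and 400 runs per scenario. None of its inputs comes from the documents:
- True freedom at day 450 is 50% or 70%, with constant hazard from day 181.
- Base withdrawal is 5%, 10% or 20%, uniform over days 182 to 450.
- 30% or 60% of recurrences are silent. Symptomatic ones are detected at onset, silent ones at the next test (day 365 or 450).
- In the related scenarios, a silent recurrence adds a chance of twice the base rate of leaving before the next test.
- Every exit is untested under the current rule. The exit ECG is assumed to find every recurrence that has occurred by then.

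Mean percent free at day 450, selected scenarios:

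| Withdrawal | Base rate | Silent | Truth | Censor at untested exit | Censor at last test | ECG at exit |
|---|---|---|---|---|---|---|
| Unrelated | 10% | 30% | 50.2 | 50.1 | 49.4 | 49.8 |
| Related | 5% | 30% | 70.5 | 71.1 | 70.8 | 70.3 |
| Related | 10% | 60% | 49.8 | 53.6 | 52.7 | 49.2 |
| Related | 20% | 60% | 49.8 | 58.2 | 56.3 | 48.8 |

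Over all related scenarios, the bias of the current rule runs from 71.1 − 70.5 = 0.6 to 58.2 − 49.8 = 8.4 points. Over all unrelated scenarios it is at most 0.2 points. Moving censoring to the last test leaves 52.7 − 49.8 = 2.9 of the 3.8 points in the third row. An exit ECG removes the upward bias and ends slightly below truth (0.6 in that row).

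**The case against.** A reader might infer that no unscheduled visit for possible recurrence needs a rhythm recording. The documents do not support that. The 3-month section asks for an ECG or other monitoring for any signs or symptoms through study end, which spans the whole evaluation period, and recurrences before it are not treatment failures (section 6.6). Section 6.7.1 also covers visits to any physician and to emergency rooms, where the study cannot order a test, so its conditional wording has a reason. What remains is a difference between the two sections that needs reconciling, and the subject who leaves without symptoms.

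A reader might also infer that untested time is scored as success, so that each hidden recurrence is worth a percentage point per 100 subjects. That is not how Kaplan-Meier works. A censored subject stays in the risk set until censoring and is then removed. The bias is material only if silent recurrence drives withdrawal, and the largest value needs a 20% base rate and 60% silent recurrence. The simulation also ignores the exits in step 2 that would be tested, which overstates the effect.

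Two further inferences fail. The waiver "If there is an Adverse Event associated with this visit, then an Unscheduled Visit CRF does not need to be completed" does not show that ECG or drug data are lost, because the CRFs are not in the documents and other sections call for this information. An off-schedule EQ-5D-5L score enters no stated analysis.

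Finally, the endpoint is descriptive, and parts of section 8 are redacted. A rule on evidence for event-free status may stand there.

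**Conclusion.** The point holds for withdrawal at a visit that does not coincide with a scheduled one, by a subject without symptoms. There the plan requires no rhythm recording and still uses the visit as the censoring date, so up to 153 days at nominal timing can enter the analysis as recurrence-free time at risk without a required test.

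The consequence is conditional. Single-procedure success is biased upward if silent recurrence makes withdrawal more likely, and hardly at all otherwise. The range of 0.6 to 8.4 points shows sensitivity to assumed inputs and is not a forecast. The plan as visible gives no means of telling which case applies; a recording at exit would. No sample size, power or error rate is affected. This is a cheap improvement to a descriptive estimate.

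**What to change.** 1. **Section 5.5 (the essential change):** require a 12-lead ECG, or another ECG recording, at any in-person exit visit, and state that a recurrence found there counts as an event.
2. **Sections 8.2.2 and 8.7 (secondary):** give one censoring rule for withdrawn subjects, by defining the event-free time point as the last rhythm-documented assessment without recurrence. Alone, this removes only part of the bias. Where withdrawal was unrelated to recurrence, it moved the simulated estimate slightly away from truth (50.1 to 49.4, truth 50.2).
3. **Section 6.7.1 and the 3-month visit section:** reconcile the conditional ECG wording in the first with the expectation in the second.

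The cost is one routine ECG at a visit that sites must already try to arrange, and slightly earlier censoring when no recording is obtained. With an exit ECG the simulated estimates fell below truth by 0.2 to 1.2 points across all scenarios, because withdrawing subjects receive an extra test. A single ECG can also miss an intermittent recurrence, so the real correction will be less complete than the simulated one.

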## Clinical Investigation Plan

### 6.7.2 Patient Reported Outcome Measures – EQ-5D-5L Questionnaires

The coordinator or designee will administer patient-reported outcome questionnaires. It is important the subject understands the meaning of all words and instructions in the questionnaires. The subject should be instructed to ask any questions about the questionnaires if further explanation is needed. Once the questionnaires are completed, the coordinator or designee will review for completeness to verify that all questions have been answered according to the directions provided.

The EuroQol Five Dimensions Questionnaire (EQ-5D-5L) patient-reported outcome measure will be collected for this trial. The EQ-5D-5L questionnaire is a standardized measure of health status that is applicable to a wide range of health conditions and treatments. It provides a simple descriptive profile and a single index value for health status that can be used in the clinical and economic evaluation of health as well as in population health surveys. EQ-5D-5L is designed for self-completion and is ideally suited for use in postal surveys, in clinics, and in face-to-face interviews and takes only a few minutes to complete. The questionnaire includes five dimensions assessing mobility, self-care, usual activities, pain/discomfort, and anxiety/depression. Each dimension is measured based on responses to 5 levels: no problems, slight problems, moderate problems, severe problems, and extreme problems. Respondents evaluate their overall health status using a visual analogue scale, which can easily be converted to quality-adjusted life years for cost utility analysis.

Note that it will not be a deviation for the EQ-5D-5L questionnaire be administered by phone. Research personnel should use the EQ-5D-5L Script for Telephone Interview questionnaire for visits conducted over the phone.

### 6.7.3 Schedule of Events

The schedule of activities specific to this clinical investigation are described in the preceding sections and are summarized in **Table 2**.

**Table 2. Schedule of PerAF APAC Clinical Investigation Activities**

Activity	Enrollment / Baseline	Procedure (~14-days of consent)	Pre-Discharge (<72 hrs post-proc.)	7-14 Day Phone Call or In-Person (7-14 days)	3-Month In-Person (91±21 days)	6-Month In-Person (181±30 days)	12-Month In-Person (365±30 days)	15-Month In-Person (450±30 days)
Informed Consent	X							
Demographics	X							
Medical History	X							
Cardiovascular History	X							
AAD & Anticoagulant Medications	X		X	X	X	X	X	X
Physical Examination	X		X					
Neurological Exam	X 		X 					
NYHA	X							
CHA 2 DS 2 VASc score	X							
12-Lead ECG	X 		X		X	X	X	X
EQ-5D-5L Questionnaire	X				X	X	X	X
24-Hour Holter	X 				X 	X 	X 	X 
Urine Pregnancy Test		(X)						
Confirm absence of thrombus		X 						

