## Clinical Investigation Plan

- PerAF APAC is a prospective clinical investigation in which the outcome is unknown at the time of enrollment
- All subjects must meet the defined eligibility criteria to minimize selection bias
- Guidance will be provided to sites regarding data collection for questionnaires
- Case report forms for data collection will be provided to sites, which will minimize inter-observer variability.
- Evaluation of the 6-month and 15-month Holter AF/AFL/AT recurrence data will be performed by an independent core laboratory.
- Adverse events will be independently adjudicated by qualified physicians.

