### 6.4 Repeat Ablation Procedures

One ablation procedure for treatment of AF/AT/atypical AFL recurrence is allowed during the blanking and therapy consolidation periods (within 180 days post-initial procedure) using the recommended parameters listed in the TactiCath SE *Instructions for Use* document. Note that recurrence and ablation of typical AFL alone does not count as a repeat procedure for AF recurrence.

Certain assessments need to be performed if a repeat ablation is required. Thrombus assessment must be performed prior to ablating the subject. Verification of the exclusion of pericardial effusion must also be performed prior to the conclusion of the procedure.

A 7-day ( $\pm$  2 days) follow-up phone call or in-person visit to the subject will be conducted after the repeat procedure. All other follow-up visits will occur as previously scheduled from the initial ablation procedure. Note that the 90-day blanking period followed by a 90-day therapy consolidation period are still in place from the initial procedure.

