## Clinical Investigation Plan

Activity	Enrollment / Baseline	Procedure (~14-days of consent)	Pre-Discharge (<72 hrs post-proc.)	7-14 Day Phone Call or In-Person (7-14 days)	3-Month In-Person (91±21 days)	6-Month In-Person (181±30 days)	12-Month In-Person (365±30 days)	15-Month In-Person (450±30 days)
Ablation procedure		X						
Assess for Pericardial Effusion		X 						
Monthly Event Recording					X 	X 	X 	X 
Adverse Event Assessment	X	X	X	X	X	X	X	X
Document Deviations	(X)	(X)	(X)	(X)	(X)	(X)	(X)	(X)
Withdrawal	(X)	(X)	(X)	(X)	(X)	(X)	(X)	(X)

(X) If applicable

1. A neurological assessment is recommended to be performed as outlined in the 2017 Consensus Statement.
2. Either a 24-hr Holter or 2 ECGs obtained ≥7 days apart may be used to demonstrate continuous AF at Baseline.
3. Thrombus assessment must be performed the day prior to or on the day of the procedure. If a thrombus is discovered, the procedure should be postponed and the subject placed on anticoagulation until the thrombus is resolved as confirmed by imaging.
4. Imaging must be performed prior to the conclusion of the procedure to exclude pericardial effusion.
5. 24-hour Holters must be obtained at the 6-month and 15-month follow-up visits. It is recommended that a 24-hour Holter be obtained at the 3-month and 12-month follow-up visits.
6. It is recommended that event recordings are collected monthly after the initial ablation procedure and whenever the subject is experiencing a symptomatic episode starting at 3-months to 15-months post-procedure as noted in the 2017 Consensus Statement.

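### Table 2 and Section 6.7 give different 6-month visit windows, and under Table 2 a required core-lab Holter can be on time yet too early to count toward 15-month success

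*Combined protocol and SAP*

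**What the plan says.** **Visit windows.** The column heading in Table 2 (Section 6.7.3) is "6-Month In-Person (181±30 days", a two-sided window. The heading in Section 6.7 is "6-Month (181 + 30 days) Follow-Up Visit", a forward-only window as printed. The 3-month visit differs in the same way: 91±21 days in Table 2 and 91 + 21 days in Section 6.7. The 12- and 15-month windows are two-sided in both places. Section 6.7.3 presents Table 2 as a summary of the sections before it, but does not say which prevails if they disagree.

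**What counts as failure.** Section 6.6 sets 90 days of blanking, 90 days of therapy consolidation and then 9 months of evaluation. It states: "Early recurrence of AF, AFL, or AT within the blanking period or therapy consolidation period will not be considered treatment failures". Section 6.4 fixes the end of the two early periods by allowing one repeat ablation "during the blanking and therapy consolidation periods (within 180 days post-initial procedure" of follow-up. Section 8.2.2 defines 15-month single-procedure success as freedom from documented recurrence "during the 9-month period following the blanking and therapy consolidation periods".

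**Required Holters.** For the 6-month visit Section 6.7 says "Administer a 24-hour Holter monitor provided by the core laboratory (required". Footnote 5 of Table 2 confirms that "24-hour Holters must be obtained at the 6-month and 15-month follow-up visits", while those at 3 and 12 months are only recommended. Section 3.2 lists this among the bias-control measures: "Evaluation of the 6-month and 15-month Holter AF/AFL/AT recurrence data will be performed by an independent core laboratory". Section 6.8 adds that the core laboratory's findings will be used in the analysis.

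**The concern.** The nominal 6-month day, 181, is the first day on which a recurrence can count. A symmetric window around it allows the required Holter to be recorded inside the consolidation period. Under Table 2, Holters on day 180 and day 181 are equally compliant, but only the second can contribute to 15-month success.

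At stake is how well recurrence is ascertained. The two core-lab Holters are the only required 24-hour recordings, and the only ones that Section 6.8 assigns to independent reading. If one is used before the evaluation period opens, an asymptomatic recurrence may go unseen or may first be documented months later. The Kaplan-Meier curve would then hold such a subject event-free for too long, which pushes the estimate towards higher success. Section 8.7 allows no imputation, so a subject with an early 6-month Holter who leaves before the 15-month visit would contribute no required Holter to the evaluation period at all.

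**Working it through.** The check is day arithmetic. No power or sample-size formula applies, because the study has no hypothesis test.

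**1. End of the non-counting period.** From Section 6.6: 90 + 90 = 180 days. This reproduces the 180 days in Section 6.4. Evaluation therefore starts on day 181, and 3 + 3 + 9 = 15 months matches the stated follow-up.

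**2. The 6-month window.**
- Table 2: 181 − 30 = 151 to 181 + 30 = 211, which is 61 calendar days. Days 151 to 180, 30 of the 61, precede day 181.
- Section 6.7 as printed: 181 to 211, which is 31 calendar days. None precedes day 181.

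**3. Required recording left if the 6-month visit falls on days 151 to 180.**
- Required Holters in the evaluation period: one 24-hour recording instead of two (24 hours against 48).
- Next required Holter, 15-month visit: 450 ± 30 = days 420 to 480. Distance from day 181: 420 − 181 = 239 to 480 − 181 = 299 days.
- Spacing between the two required Holters: 420 − 180 = 240 to 480 − 151 = 329 days.
- Next scheduled required rhythm recording, the 12-month 12-lead ECG: 365 ± 30 = days 335 to 395. Distance from day 181: 335 − 181 = 154 to 395 − 181 = 214 days.

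**4. Comparison under Section 6.7 as printed.** A required Holter and a required ECG both fall 0 to 30 days after day 181.

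**5. The 3-month visit.** Table 2 gives 91 − 21 = 70 to 91 + 21 = 112, and Section 6.7 gives 91 to 112. No required Holter is attached to this visit. Day 112 is still before day 181, so a recording made at the visit lies in the non-counting period under either window. The mismatch should be tidied up but does not affect the success estimate.

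**6. Number of subjects affected.** This would need the distribution of actual visit days, which the documents do not give. No count is derived.

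**The case against.** **Section 6.7 may already be the rule.** Table 2 is described as a summary, and the text it summarises puts the visit on or after day 181. The bare plus sign appears only at days 91 and 181, each the first day after a 90-day period, where a forward-only window makes sense. That points to a symbol slip in the table rather than a deliberate choice. This is a fair reading and is why the point is classed as an inconsistency. However, the plan does not say which place prevails, and sites may well work from the table.

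**The plus sign may be a text-reading error for ±.** This is possible, although the 12- and 15-month headings in the same section kept the ± sign. If so, the text and the table agree, but both then straddle day 181 and the early Holter remains possible.

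**Other monitoring exists.** From the 3-month visit onward, signs or symptoms of recurrence should lead to an ECG (Section 6.7), and unscheduled visits for possible recurrence are documented (Section 6.7.1). A 12-month Holter and monthly event recordings are recommended. A reader might infer that nothing checks rhythm between day 180 and the 12-month ECG. The documents do not support that: the gap is in scheduled, required recordings. What remains exposed is mainly asymptomatic recurrence. If it persists to month 12 or 15 it is dated late; if it resolves before then it may be missed.

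**Two further inferences to avoid.**
- Days 151 to 180 are about half of the Table 2 window (30/61 = 49%). That is a share of calendar days, not of subjects.
- Section 4.1.1 says that serious recurrences count as effectiveness failures and gives no start day, which could be read as conflicting with Section 6.6. That sentence serves to keep such events out of the safety endpoint. Sections 6.6 and 8.2.2 supply the timing and agree with each other. Section 7.1.1.1 mentions a primary effectiveness endpoint whose definition is not visible in the redacted text. At most this is a matter of wording, and it is not part of the point.

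**Conclusion.** The point holds as a minor internal inconsistency. A site that follows Table 2 can record one of the two required core-lab Holters on days 151 to 180, where on the visible text it cannot contribute to 15-month single-procedure success. For such a subject the remaining required Holter comes 239 to 299 days after day 181, and the next scheduled required rhythm recording comes 154 to 214 days after it. The likely direction of error is overstated success, through asymptomatic recurrence missed or dated late. The size of that error cannot be stated.

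The conclusion assumes that sites may use the Table 2 window and that no redacted text defines a different start of evaluation. The endpoints are non-powered (Section 4.0), no hypothesis is tested (Section 8.2) and pass/fail criteria do not apply (Section 8.10), so type I error and power are not involved. The estimate still deserves care, because Section 1.1.2 intends these data to supplement Persist-End in support of a persistent AF indication.

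**What to change.** Reconcile the 3- and 6-month windows between Table 2 and Section 6.7, so that both places require the 6-month core-lab Holter to be recorded on or after day 181. Send sites a short notice of the window. In the report, give the number of subjects whose required 6-month Holter was recorded before day 181 and the number recorded on or after it.

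The cost is a few words in the plan, one site notice and one line in a report table. A Holter already recorded on days 151 to 180 cannot be recovered for the evaluation period; it can only be counted and disclosed, so the change is worth most if made early.
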